In summary, we anticipate that a 12-week program of exercise rehabilitation will increase muscle mass and improve skeletal muscle function and that this is mediated by several different processes that we aim to identify. In this regard we expect that basal anabolic signaling will be higher in the resting muscle of the regular exercise group versus the resting muscle of the usual care group, *a potential carry over effect of regular exercise*. In addition, we anticipate that while the high calorie whey supplement will cause an increase in anabolic signaling in the resting muscle of both groups, the response will be greater in the regular exercise group, *again possibly reflecting a carryover effect of regular exercise*. *If a carryover effect is indeed present, then this would support the hypothesis that regular exercise is beneficial even in ESRD*. We also anticipate that acute exercise alone will increase anabolic signal transduction, and that this response will be enhanced by the high calorie whey supplement. If true, **this holds the prospect of developing a simple therapeutic strategy to boost the anabolic response to regular exercise and thereby enhance the functional and cardiopulmonary benefits of exercise in patients with ESRD**.

Detailed Protocol for Nutrient Supplementation, Acute Exercise, and Biopsy for Specific Aim 2. An outline illustrating the acute exercise, biopsy, and nutrient supplementation protocol for Specific Aim 2 is presented in Figure 2. On a morning the day before regular MHD and after an overnight rest, both regular exercise and usual care subjects will consume a light protein-free breakfast between 7 and 8 am and will be studied three hours later after a 60-min rest. Subjects in both groups will then begin a unilateral dominant lower limb exercise session lasting \approx 15 min, with the contra-lateral limb at rest. At the start of the exercise session, subjects will ingest half the high calorie whey or placebo so as to compensate for AA deficiencies common in MHD subjects. The other half of the supplement will be ingested at the end of the exercise session so as to enhance anabolic signal transduction. This will be followed by 60 minutes of rest, then muscle biopsies will be performed on both limbs to assess anabolic signal transduction.

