Secondary analyses, Specific Aim 2. In this specific aim we will analyze molecular changes in muscle biopsied at baseline and at the end of the study. IGF-1 is a key muscle growth factor; Kopple et al (45) reported that IGF-1Ea mRNA levels rose ~100% in 12 MHD subjects undergoing 21.5 weeks of combined resistance and endurance exercise. We plan to compare changes in IGF-1 mRNA levels from baseline to those levels at the end of 12 weeks of rehabilitation or usual care. Muscle will be obtained from limbs at rest in the exercise and usual care subjects as described above (n=12/group) and we will consider a 50% change in IGF-1Ea mRNA to be a clinically meaningful difference. While there are no data available in MHD subjects to estimate the standard deviation of the change in these molecular indices from baseline, Appendix VIII may be used to estimate the power associated with an assumed standardized effect size that is small (0.3), medium (0.5) or large (0.8).

Secondary analyses, Specific Aim 2A. In this specific aim we will assess the nutrient-enhanced exercise-induced protein signal transduction pathway in subjects undergoing exercise versus usual care. Specifically, we will compare the change in activity (phosphorylation) of the mTOR signal transduction pathway induced by unilateral exercise alone versus unilateral exercise plus nutrient supplementation. This will be a pilot study of 12 subjects in each group. Since this is a novel measurement and there are no data in MHD subjects describing the variance of this response, a power analysis has not been carried out. Change in activity will be taken to equal the difference in activity between the unilateral exercise limb and the contra-lateral resting limb of the same subject. We will also examine the effect of the supplement alone vs. placebo on signal transduction in the resting limb of unilateral exercise and usual care subjects. Of note, Hulmi (71) reported that whey protein enhanced exercise-induced signaling (phosphorylated p70S6K)

by nearly 5-fold over exercise alone in young healthy subjects, while Drummond (73) noted a similar increase in the elderly following EAA ingestion.

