Statistical analysis plan. Comparisons of clinical and demographic data between groups at baseline will be performed by the appropriate statistical test (for continuous variables, t-test for normally distributed data and Wilcoxon test for non-normal data; for categorical variables, chi-square test or Fisher's exact test). These comparisons will be performed at baseline only to assess adequacy of randomization. Comparisons between groups for cardiopulmonary exercise test, muscle biopsy, energy expenditure, cognitive function, and other functional measures before and after the study period will be performed by multivariate ANOVA; post-hoc comparisons will be made using the Bonferroni method. To analyze continuous variables measured at three or more time points we will use linear mixed effects regression (114). To explore the relationships between a given outcome and other variables, we will use multiple regression techniques. Since the reliability of a fitted regression model may be reduced if too many predictors are used (114), we will limit the number of predictors to four variables in each model ($\leq 1/10$ of the total). For the primary outcome, change in peak VO_2 , the specific independent variables in the model will include exercise compliance (average energy expended in kcals/week), change in muscle strength, and change in muscle mass. Missing data will be managed using the multiple imputation method which is preferable to older methods and described in detail by Schafer & Olsen (1999).

For Specific Aim 2 (effect of acute and chronic exercise on muscle wasting), we will employ a linear model, using period (baseline vs. 4 months) and treatment (exercise training vs. usual care) as independent variables along with their interaction (Bonferroni method). The intention to treat principal will be applied for all analyses.

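### The Aim 2 biopsy model states no within-subject pairing; adjusting for the baseline biopsy should be named as the single training-effect analysis, and the limb and period wording reconciled

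*Combined protocol and SAP*

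**What the plan says.** Four parts of the combined protocol and SAP bear on the Aim 2 training effect in muscle.

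- **Statistical analysis plan, Aim 2 paragraph.** The analysts will "employ a linear model, using period (baseline vs. 4 months) and treatment (exercise training vs. usual care) as independent variables", together with the interaction. The paragraph labels the aim as covering both acute and chronic exercise.
- **Statistical analysis plan, general paragraph.** Comparisons between groups for "muscle biopsy, energy expenditure, cognitive function, and other functional measures before and after the study period will be performed by multivariate ANOVA". Mixed models have a separate scope: "To analyze continuous variables measured at three or more time points we will use linear mixed effects regression".
- **Secondary analyses, Specific Aim 2.** "We plan to compare changes in IGF-1 mRNA levels from baseline to those levels at the end of 12 weeks". The samples are from resting limbs, 12 per group. No SD of the change is available, and no power figure is derived.
- **Approach to Specific Aim 2, question 1.** The resting dominant limb is compared between placebo recipients in the exercise group (Group 1) and the usual care group (Group 3). Baseline is not mentioned and no test is named.

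On the samples, the Approach to Specific Aim 2 takes one biopsy per limb: dominant after exercise, non-dominant after rest. The detailed protocol agrees: "Subjects in both groups will then begin a unilateral dominant lower limb exercise session lasting" about 15 minutes. General study design, the biopsy procedure and the Aim 2 power section all put the end-of-study biopsy at 12 weeks.

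For the supplement comparison (Aim 2A), change in activity is the "difference in activity between the unilateral exercise limb and the contra-lateral resting limb of the same subject".

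**The concern.** Each subject gives a biopsy at baseline and another at the end, so the two values are presumably correlated. The model sentence has no subject term, change score or covariance structure. The repeated-measures method that the plan does name is reserved for three or more time points, and the biopsies have two periods. An analyst could follow the model sentence, the multivariate ANOVA, the change comparison or the end-of-study comparison of question 1, and in each case claim to follow the plan.

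At stake is precision in a small, invasive sample. Ignoring a positive correlation makes the standard error of the interaction too large, so a real training effect is more likely to be missed.

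Two wording conflicts stand apart from this. The sub-study yields no resting sample from the dominant limb, because that limb is exercised and biopsied once. And the model's second period is 4 months where the design has 12 weeks.

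**Working it through.** **Figures in the plan.** There is no Aim 2 power figure to reproduce. The primary-endpoint figure does reproduce: a two-sample t-test with standardized effect 17/20 = 0.85, two-sided 0.05, has power 0.805 with 23 per group and 0.786 with 22. It is not affected by this point.

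**Inputs.** n = 12 per group (Secondary analyses, Specific Aim 2), taken as the subjects entering the training comparison; fewer would lower every power below. Two-sided 0.05. The within-subject correlation ρ is not in the documents, so I assume 0, 0.3, 0.5 and 0.7. Baseline and end values are taken as bivariate normal with equal variance, σ = 1.

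**Formulas.** The period-by-treatment interaction equals the difference between groups in mean change.

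- True standard error: √(4(1−ρ)/n). At ρ = 0.5: √(4 × 0.5/12) = 0.408.
- Standard error that independent errors would report: √(4/n) = √(4/12) = 0.577.
- Ratio: 1/√(1−ρ) = 1.00, 1.20, 1.41, 1.83 for ρ = 0, 0.3, 0.5, 0.7.
- Change-score power for a 1 SD effect at ρ = 0.5: noncentrality 1/0.408 = 2.45 on 22 df, power 0.65.
- ANCOVA variance relative to the change score, before the small cost of estimating the slope: [2(1−ρ²)/n] / [4(1−ρ)/n] = (1+ρ)/2 = 0.50, 0.65, 0.75, 0.85.

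**Simulation** (at least 60,000 replicates per cell; effects in SDs of a single measurement):

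| | ρ = 0 | 0.3 | 0.5 | 0.7 |
|---|---|---|---|---|
| Type I error, literal model | 5% | 2% | 0.7% | 0.1% |
| Power for 1 SD, literal model | 0.40 | 0.38 | 0.36 | 0.33 |
| Power for 1 SD, change score | 0.38 | 0.51 | 0.65 | 0.86 |
| Power for 1 SD, ANCOVA | 0.63 | 0.67 | 0.75 | 0.89 |
| 95% CI half-width, literal model | 1.16 | 1.16 | 1.16 | 1.15 |
| 95% CI half-width, change score | 1.18 | 0.99 | 0.84 | 0.65 |
| 95% CI half-width, ANCOVA | 0.86 | 0.82 | 0.74 | 0.61 |

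Type I error for the change score and ANCOVA is about 5% throughout. At ρ = 0.5 the literal model loses (0.649 − 0.360)/0.649 = 45% of the change score's power. For the plan's large effect, 0.8 SD of the change, power at ρ = 0.5 is 0.20 literal, 0.47 change score and 0.56 ANCOVA.

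**Passages side by side.**

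- *Limb.* Question 1 compares resting dominant limbs. The Approach and the detailed protocol exercise the dominant limb and rest the other, with one biopsy each. The two cannot both describe the sub-study samples.
- *Period.* 4 months is 4 × 365.25/12/7 = 17.4 weeks, about 5 weeks after the 12-week biopsy.
- *Supplement.* The Aim 2 summary expects that "the high calorie whey supplement will cause an increase in anabolic signaling in the resting muscle of both groups". A resting sample taken after the supplement therefore carries a supplement effect unless the comparison is kept to placebo recipients, as question 1 does and the model sentence does not.

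**The case against.** The strongest reply is that pairing is plainly intended. The Aim 2 power section compares changes from baseline and speaks of the SD of the change, which is a within-subject quantity. The before-and-after multivariate ANOVA can be read as paired too. The model sentence never says independent errors, and with a subject term its interaction is the same test as the change comparison. This stands: a reader might infer that the plan ignores pairing, and the documents do not support that. They support only that the governing sentence omits it.

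Several further limits also stand.

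- The correlation, normality and equal variances are assumptions. The plan frames its IGF-1 effect as a 50% change, so the scale is open.
- The change score is a valid analysis; preferring ANCOVA is a gain in efficiency, not the correction of an error.
- The model sentence contains no limb wording. The limb conflict lies between question 1 and the biopsy protocol.
- The limb of the baseline biopsy is unstated in the text available. That is a silence, not a contradiction, and the figures and appendices are not shown.
- It is tempting to say that no resting dominant sample exists at the end of study. General study design gives biopsies at 12 weeks and then, additionally, sub-study biopsies two to three days later, so a separate 12-week biopsy is a possible reading.

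What the reply does not remove is that one analysis should be named, and that ANCOVA improves even on the correctly paired change score.

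**Conclusion.** The point holds as a gap in specification with a conditional cost. If the Aim 2 model is fitted with independent errors, the interaction estimate is unbiased and its test conservative: at ρ = 0.5 and 12 per group, type I error is about 0.7% and power for 1 SD about 0.36 instead of 0.65. At ρ = 0 nothing is lost, and if a subject term is intended the loss disappears. A reader might infer bias or excess false positives in the training-effect test; neither follows.

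The gain from baseline adjustment does not depend on how the sentence is read. ANCOVA had more power than the change score at all four correlations, by 0.25 at ρ = 0 and 0.03 to 0.04 at ρ = 0.7, under the normal, equal-variance assumptions above.

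The limb conflict and the 4-month label need no assumption. The label changes nothing in a two-level period factor but should agree with the design. Aim 2 is secondary and partly pilot, so this should be put right but does not threaten the trial's main conclusion.

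**What to change.** In the statistical analysis plan, name one Aim 2 training-effect analysis: ANCOVA of the end-of-study resting-limb value on training group, with the baseline-biopsy value as covariate. This replaces both the period-by-treatment model and the multivariate ANOVA for that question. If the end-of-study sample is the sub-study biopsy taken after the supplement, carry over the restriction to placebo recipients from question 1. Keep the exercised-minus-resting difference within subject for the acute and supplement effects, and take acute exercise out of the period-by-treatment wording.

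In the protocol text:

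- reconcile the resting dominant limb of question 1 with the Approach and detailed protocol;
- reconcile 4 months with 12 weeks;
- state which limb is biopsied at baseline, so that the resting samples are comparable;
- state whether the 12-week biopsy in General study design is separate from the sub-study biopsy.

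The cost is wording, with the same biopsies and no added procedure. ANCOVA uses one degree of freedom. Against a simple comparison of end values it is slightly weaker at ρ near 0 (0.63 against 0.65 for 1 SD), level at about 0.2 and stronger above that.

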Figure 6. Bar graphs showing 42% increase in exercise time in the exercise group and no change in usual care subjects following 1-year of exercise training in patients with abdominal aortic aneurysm disease (86). Changes in exercise capacity were similar at the completion of the full trial, after up to 3 years of home-based exercise training.

Data on the approach to activity monitoring and surveillance. In the current proposal, methods for monitoring and surveillance of physical activity will be employed that are similar to the above-mentioned ongoing NIH trial. In our NIH trial, we observed that subjects achieved $98\pm 7\%$ of their target heart rates during monitoring (87). Using 7-day activity recall instruments to quantify weekly activity, the mean overall energy expenditure for subjects in the exercise group after 1 year of participation was 2269 ± 1207 kcals/week (shown in the figure below). This is roughly double the CDC/AHA recommendations for physical activity, and is significantly higher than the recently-published HF-ACTION trial (≈ 500 kcals/week) and other rehabilitation studies. This degree of exercise stimulus resulted in a 42% increase exercise capacity on the 1-year treadmill test, while no changes were observed in controls. Thus, the approach proposed is likely to be successful in achieving an adequate training stimulus.

[figure not shown]

Figure 7. Average energy expenditure over 1 year in the exercise group (from reference #86)

Studies on muscle wasting in kidney failure. [name] (Co-PI) is a Professor of Medicine, Emeritus Active at Stanford University, and a Staff Nephrologist at the Palo Alto VAHCS. The focus of his research is on the mechanisms of muscle wasting in CKD with the goal of identifying potential strategies for the prevention and treatment of this disorder. The current proposal reflects an effort to translate his many animal findings to a clinical population with CKD. The following briefly highlights some of this work relevant to the current proposal.

Chronic uremia attenuates growth hormone induced signal transduction in skeletal muscle. Sun D, Zheng Z, Tummala P, Oh J, Schaefer F, **[name] R**: *J Am Soc Nephrol* 15:2630-6, 2004. Resistance to growth hormone contributes to muscle wasting in uremia. To test whether impaired growth hormone signaling is a cause of the resistance to growth hormone and to elucidate its mechanisms, we studied

muscle growth hormone signaling and action in rats with surgically induced chronic renal failure. As we observed previously, growth hormone stimulated IGF-1 expression was depressed in CRF and evidence is provided that the resistance to growth hormone is caused at least in part by impaired JAK2-GHR-STAT5 phosphorylation and nuclear STAT5 translocation. Furthermore, this study demonstrated that the attenuated JAK2 –STAT5 signaling may be caused by at least two different processes. One involves depressed phosphorylation of the signaling proteins because of increased suppression of cytokine signaling-2 expression that may be linked to low-grade inflammation. The other may involve increased signaling protein dephosphorylation because of heightened protein-tyrosine phosphatase activity.

Work-induced changes in skeletal muscle IGF-1 and myostatin gene expression in uremia. Sun DF, Chen Y, **[name] R.** Kidney Int 70:453-9, 2006. Resistance to GH induced IGF-1 gene expression contributes to uremic muscle wasting. Since exercise stimulates muscle IGF-1 expression independent of growth hormone, we tested whether work overload could increase skeletal muscle IGF-1 expression in uremia and thus bypass the defective growth hormone action. In addition, to provide insight into the mechanism of uremic wasting and the response to exercise we examined myostatin expression. Unilateral plantaris muscle work overload was initiated in uremic and paired normal rats by gastrocnemius tendon ablation with the contralateral plantaris as a control. Some rats were growth hormone treated for 7 days. Work overload stimulated a gain in weight of the plantaris muscle in both groups and corrected the uremic muscle atrophy. As shown in Figure 8 below, growth hormone increased plantaris IGF-1 mRNA levels >2 fold in paired rats but the response in chronic renal failure was severely attenuated.

[figure not shown]

Fig 8. Effect of GH on muscle IGF-1 mRNA levels

[figure not shown]

Fig 9. Effect of work overload on muscle IGF-1 mRNA levels

Work overload increased the IGF-1 mRNA levels significantly in both the chronic renal failure and paired groups, albeit less brisk in renal failure (Figure 9). However after 7 days IGF-1 mRNA levels were elevated similarly, >2 fold, in both groups. Of note, the atrophied uremic plantaris muscle basal myostatin mRNA levels were increased significantly and normalized after an increase in work-overloaded rats suggesting a myostatin role in the wasting process (Figure 10).

[figure not shown]

Fig 10. Myostatin levels in CRF and response to work overload

In summary, these findings provide insight into the mechanisms of skeletal muscle wasting in uremia and the hypertrophic response to exercise, and suggest that alterations in the balance between IGF-1 and myostatin play an important role in these processes.

Increased workload fully activates the blunted IRS-1/PI3-kinase/Akt signaling pathway in atrophied uremic muscle. Chen Y, Sood S, Biada J, Roth R, **[name] R.** Kidney Int. 2008. In this study of muscle wasting and recovery in chronically uremic rats, we set out to characterize the mechanisms whereby resistance exercise increases muscle mass, despite the presence of impaired signaling through the IRS-1/PI3-kinase/Akt pathway and insensitivity to IGF-1. Uremic and sham nephrectomized (SN) rats with surgically induced unilateral plantaris muscle work overload were studied, with the contralateral plantaris muscle serving as a nonloaded control. In these control muscles signaling protein levels were similar in the chronic renal failure and SN groups despite atrophy of the chronic renal failure muscle. However, basal state activation (phosphorylation) of the IRS-1/PI3-kinase/Akt signaling pathway was depressed in the uremic rat muscle. Of note, even though the basal activity of the IRS-1/PI3-kinase/Akt signaling pathway was depressed in the uremic atrophied plantaris muscle, simply increasing the muscle workload effectively activated this signaling pathway and phosphorylation of the signaling proteins in the work-overloaded plantaris muscle was similar in both groups of rats (Figure 11 below). Work overload induced a significant increase in local IGF-1 and mechano-growth factor expression and also a significant increase in signaling protein levels. Together these changes provide an explanation for the work-induced increase in signal transduction. Importantly, the work-induced signaling response in the uremic rats was similar to that observed in non-uremic rats and promoted changes that we observed consistent with a decrease in muscle protein degradation, an increase in protein synthetic capacity and an increase in myonuclear number.

[figure not shown]

Fig 11. Levels of phosphorylated signaling protein levels in control and work overloaded plantaris muscle of SN (sham nephrectomy) and chronic renal failure rats. Phosphorylation of IRS-1 and Akt is depressed in the control (con) non-loaded muscle of the renal failure group. Work overload stimulated signaling protein phosphorylation similarly in both groups of rats.

We concluded that increasing the work of atrophied muscle in uremia can fully activate the depressed **basal IRS-1/PI3-kinase/Akt signaling pathway and it appears to do so by increasing IGF-1 and mechano growth factor expression and increasing the levels and phosphorylation the IRS-1/PI3 kinase/Akt/ mTOR signaling proteins.** This in turn appears to account for the increase in the reduced uremic muscle mass, which reached a level comparable to that seen in normal rat.

Leucine stimulated mTOR signaling is partly attenuated in skeletal muscle of chronically uremic rats. Chen Y, Sood S, McIntire K, Roth R, **[name] R.** Am J Physiol Endocrinol Metab. 2011. The branched chain amino acid leucine stimulates muscle protein synthesis in part by directly activating the mTOR signaling pathway. Furthermore, leucine, if given in conjunction with resistance exercise, enhances the exercise-induced mTOR signaling and protein synthesis. In this study we tested whether leucine can activate the mTOR anabolic signaling pathway in uremia and whether it can enhance work overload-induced signaling through this pathway. CKD and control rats were studied after 7 days of surgically induced unilateral plantaris muscle work overload and a single leucine or saline load. In the basal state 4E-BP1 phosphorylation was modestly depressed in non-work overload muscle of CKD rats while rpS6

phosphorylation was nearly completely suppressed. After oral leucine mTOR, S6K1 and rpS6 phosphorylation increased similarly in both groups while the phospho-4E-BP1 response was modestly attenuated in CKD. In work overload CKD muscle leucine augmented mTOR and 4EBP1 phosphorylation, but its effect on S6K1 phosphorylation was attenuated and it failed to stimulate rpS6 phosphorylation.

In summary, this study has established that the chronic uremic state impairs basal signaling through the mTOR anabolic pathway, an abnormality that may contribute to muscle wasting. ***However despite this abnormality, leucine can stimulate this signaling pathway in CKD***, though its effectiveness is partially attenuated, especially in skeletal muscle undergoing sustained work overload. Thus, even though there is some resistance to leucine in CKD, these results suggest a potential role for leucine rich supplements in the management of uremic muscle wasting.

Description of key relevant studies published by co-investigators.

[name] (Co-Investigator) is [name] /Nephrology and Chief of Nephrology at Stanford University and a leader in the field of outcomes research in CKD. [name] (Co-Investigator) is a Staff Nephrologist/Gerontologist VAPAHS and Assistant Professor of Medicine/Nephrology at Stanford University. She is a widely recognized authority on cognitive disorders in the CKD population. Some representative studies relevant to the current proposal are presented below.

Cognitive impairment in chronic kidney disease. **Kurella-Tamura M, Chertow GM, Luan J, and Yaffe K.** J Am Ger Soc; 52:1863-1869, 2004. The prevalence of cognitive impairment and its association with the severity of kidney disease has not been defined. A cross-sectional study of cognitive function was performed in 160 ambulatory persons with ESRD and CKD not yet on dialysis. The performance on three cognitive function tests assessing global cognitive function (3MS), executive function (Trails B), and verbal memory (California Verbal Learning Trial, or CVLT) was compared to published norms. Overall, 17% of subjects met established criteria for global cognitive impairment. Global impairment was present in 27% with ESRD and 15% with advanced CKD, but in no subjects with mild to moderate CKD ($p=0.02$). Unadjusted and adjusted mean scores on the 3MS, Trails B, and CVLT immediate and delayed recall were significantly worse for subjects with ESRD than for subjects with CKD or published norms ($p<0.001$ for all comparisons). Scores on the Trails B ($p<0.001$) and CVLT immediate ($p=0.01$) and delayed recall ($p<0.001$) were significantly worse for subjects with CKD not requiring dialysis than for published norms. In addition, the fraction of subjects with impairment on the 3MS and Trails B increased with decreasing kidney function. These results demonstrate that significant impairment in cognitive function is present in both CKD and ESRD, and suggest kidney disease directly contributes to cognitive impairment.

Significance of frailty among dialysis patients. **Johansen KL, Chertow GM, Jin C, Kutner NG.** J Am Soc Nephrol. 2007 Nov;18(11):2960-7. The aim of this study was to determine the prevalence and predictors of frailty among a cohort of incident dialysis patients and to determine the degree to which frailty was associated with death and hospitalization. A cohort of 2,275 adults was studied who participated in the Dialysis Morbidity and Mortality Wave 2 study, of whom two-thirds met our definition of frailty: a composite construct that incorporated poor self-reported physical functioning, exhaustion/fatigue, low physical activity, and undernutrition. Multivariable logistic regression analysis suggested that older age, female sex, and hemodialysis (rather than peritoneal dialysis) were independently associated with frailty. Cox proportional hazards modeling indicated that frailty was independently associated with higher risk of death (adjusted hazard ratio [HR] 2.24, 95% confidence interval [CI] 1.60–3.15) and with the combined outcome of death or hospitalization (adjusted HR 1.63, 95% CI 1.41–1.87). Therefore, frailty is extremely common and is associated with adverse outcomes among incident dialysis patients. Given its prevalence and consequences, increased research efforts should focus on interventions aimed to prevent or attenuate frailty in the dialysis population.
